Posters displayed on admitting wards notify parents and patients that the centre is participating in a national service evaluation of children's bone and joint infections. Parents will have the opportunity to inform a member of their child's care team if they do not want their child's information entered into the database.

Sample size calculations

The study is funded to enable a maximum of 1,000 cases of OM or SA to be entered into the database. In order to get an accurate national evaluation, all participating centres will be asked to record cases for at least six months. It is estimated that at least 500 cases will be accrued by around 50 centres over a 6-12 month period. All eligible cases at participating centres will be recorded.

Data Collection

We will record demographic details and details of hospitalisation(s) including transfers between hospitals; type and site of disease; routine haematology, biochemistry and microbiology; radiological procedures; surgical procedures; length of IV therapy; antimicrobials used, route and duration; reason/criteria; used for oral switch (if any); and clinical outcomes at 3 months.

These data are to be collected from the patients' clinical notes. Training will be provided for teams at participating centres. The study will use a password protected web based data collection form that can be accessed at all participating hospitals.

Study Objectives

The study has three major objectives:

1. What are the clinical, biochemical and radiological criteria used by UK paediatricians / orthopaedic surgeons / radiologists to diagnose osteomyelitis?
2. What is the range of durations of intravenous and oral antibiotics used to treat osteomyelitis? What factors affect durations (e.g. surgery / blood tests / microbiology results).
3. What are the rates of treatment failures / complications for different:
 - (a) Antibiotic regimes used at participating centres?
 - (b) Surgery types used at participating centres?

and what actions were taken following a complication at participating centres?

These objectives are broken down into further sub-objectives:

- 1A:** Describe the study sample: demographics; past medical history; presenting limbs/joints affected; and diagnosis types aiming to identify factors predisposing children to bone and joint infections. Describe pre-presentation variables that affect drug choice, dosage and duration, in particular age, allergies and co-morbidities.

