Any children not falling into any of these categories will be excluded from the analysis.

Definitions

1. Simple cases

Children presenting with SA or OM for the first time, and with no chronic comorbidities. Specifically:

- No orthopaedic surgery 6 months prior to presentation on same limb/joint
- No chronic co-morbidities (sickle cell disease, known immunocompromise, indwelling central venous catheter or PICC, cystic fibrosis, or cerebral palsy).

2. Complex cases

Children presenting with SA or OM who already have a diagnosis of SA or OM and/or have chronic comorbidities, but who are not presenting because of an infected implant from previous orthopaedic surgery. Specifically:

- Not presenting because of an infected implant
- Any orthopaedic surgery in 6 months prior to presentation on same limb/joint
- Any chronic co-morbidities (sickle cell disease, known immunocompromise, indwelling central venous catheter or PICC, cystic fibrosis, or cerebral palsy).

3. Infected implants

Children presenting with SA or OM who already have a diagnosis of SA or OM and who are presenting because of an infected implant from previous orthopaedic surgery.

4. Incorrect diagnosis of SA/OM

Some children captured by the database were treated for SA/OM but were later found to have a different diagnosis.

Completeness of follow-up

Follow-up data are collected at a follow-up visit at around 3 months post discharge. The number lost to follow up will be reported and the reasons where known will be documented. Any deaths and their causes will be reported separately.

Study Outcomes

This study examines many measurements routinely made in the diagnosis, treatment, and aftercare of children with SA or OM. There are three areas of key interest: Diagnosis (Objective 1); Treatment (Objective 2); and Complications Arising and/or Treatment Failures (Objective 3). The key endpoints are:

Diagnosis:

- Bones and joints affected
- Time taken from first presentation to:
 1. Referral to hospital
 2. Having surgery
 3. Initiation of IV antibiotics [this time-point used also as a proxy for a diagnosis being made]
- Surgical procedures carried out prior to diagnosis
- Imaging types used (X-ray, CT scan, ultrasound, bone scan, MRI), and results obtained
- Diagnostic blood tests carried out (Hb, WBC, N, Plt, CRP, ESR) and their outcomes
- Microbiological tests carried out (presence of any of 8 named micro-organisms)

Antibiotic Treatment in and post hospital stay:

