The number and percentage of types of sample for micro-biological testing (e.g. blood, pus, etc.) that are typically taken from children will be reported [see Table 1D-2].
- [1E] The number and percentage of cases with test results at presentation for: each of 6 blood tests; and the combinations ‘CRP & ESR’ and ‘CRP & no ESR’ will be reported, split by centre type (Tertiary / Secondary) [see Table 1E-1]. A boxplot for each of the six blood test measures at presentation will be created to show the distribution of results. Proportions with elevated results (above centre-specific normal ranges) will be calculated for each blood test type [see Table 1E-2].

The blood test result ‘CRP_{max}’ will be summarised for culture-positive and culture negative cases and a box plot created to compare these. This analysis will be split by age-group. This is to explore whether a higher CRP_{max} is associated with particular organisms. Differences that are clinically significant will be tested for statistical significance using appropriate hypothesis tests [see Table 1E-3].
- [1F] There are five imaging methods that could be requested by clinicians to aid diagnosis. The number and percentage of cases for each imaging type used prior to diagnosis will be reported, split by centre type (Tertiary / Secondary) and of these the number and percentage abnormal [see Table 1F-1].

Objective 2

Treatment of children with SA or OM takes the form of antibiotic treatment and additionally for some cases, surgical intervention. Initially antibiotics are given intravenously. At a later date, antibiotics are given orally – the timing of the switch is based on clinical judgement that the child has recovered sufficiently and is capable of taking drugs orally.

- [2A] The lengths of time on IV antibiotics, oral antibiotics, and total antibiotic duration will be summarised using appropriate descriptive statistics. (Note that these times are based on what happened during hospital stay and what was **planned** at discharge. It is not possible to obtain data for the actual date when antibiotics were stopped post discharge.) Results will also be split by centre type, whether there was at least one surgical procedure after initiation of IV antibiotics, if CRP_{max} occurred at presentation, and by microbes detected. [See Table 2A-1].

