Antibiotic regimes will be further summarised for the sample: Number of antibiotics given in the initial treatment; timing of oral switch (<1 wk, 1-2 wks and >2 wks)); total course of antibiotics (shortened vs standard); dose (augmented at least once vs standard dose throughout where ‘augmented at least once’ is defined as having at least one high dose of IV antibiotics); and total number of different antibiotics prescribed over the full treatment period [see Table 2A-2].

- [2B] Antibiotics prescribed during hospital stay will be summarised using frequencies and percentages. There are a large number of antibiotics that could be prescribed by either route. Of these, 4 named IV antibiotics and 5 named oral antibiotics are of particular interest. A category labelled ‘other’ will be used to define all other antibiotics given by each route. For each antibiotic and route, summary statistics will be reported for whether it was part of the initial prescription; given at least once; frequency of administration of doses during a day; daily dose per kg weight of child; and duration of course (> 1 week Y/N). This will give an overview of the most commonly prescribed antibiotics during hospital stay [see Table 2B-1].

Initial IV antibiotic prescriptions will be compared between secondary and tertiary site types; between children with and without penicillin allergy; and with and without sickle cell disease [see Table 2B-2].

- [2C] Blood test results are routinely used to aid the decision to stop giving antibiotics via IV (ie. oral switch). The combinations of blood tests carried out immediately prior to (on the day before or on the day of) the oral switch will be reported as numbers and percentages. CRP as a proportion of CRP_{max} will be summarised [see Table 2C-1].

The change in blood test results over time will be explored graphically using boxplots. For each blood test type, a plot will be produced showing the distribution of results at: presentation; initial of IV; and on each day following start of IV.

- [2D] The number and percentage of cases undergoing different types of surgery post diagnosis will be reported [see Table 2D-1].
- [2E] Appropriate summary statistics will be used to describe length of hospital stay for cases – overall, and split by age-group and centre type [see Table 2E-1].
- [2F] The number and percentage of cases with imaging after initiation of IV will be reported split by site type and image type, with results given.

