Other

Infection History in the last 12
calendar months?

Pneumonia

Septicaemia

Pyelonephritis

Cellulitis / soft tissue infection

Meningitis

Osteoarticular infection

Abdominal sepsis

Varicella

Other

History of Trauma in the last
month?

Other Surgery in 12 months prior to
presentation?

Pre-presentation variables that affect drug choice, dosage and duration. (Simple cases only)

TABLE 1A-7

Antibiotic Medical History	N(%)	Route		Duration
		IV	Oral	> 1 week
Penicillin allergy		-	-	-

Antibiotics (1 month
pre-presentation)

Any

Flucloxacillin

Clindamycin

Cefuroxime

Ceftriaxone

Amoxicillin

Co-Amoxiclav

Rifampicin

Vancomycin

Fusidic Acid

Teicoplanin

Other

1B: The clinical time-line for diagnosis

TABLE 1B-1

Diagnostic and hospital stay Time-line (Days)	Appropriate Summary Statistics
From first presentation to:	
Hospital Referral	
1 st Imaging	
Pre-diagnosis surgery	
Radiological diagnosis	
Initiation of IV antibiotics	
(proxy for diagnosis of OM/SA)	

1C: Surgical procedures carried out post presentation and prior to diagnosis (before or on the same day as initiation of IV antibiotics).

TABLE 1C-1

Surgery types	Rate n (%)
Any	
Aspiration	
Incision and drainage	
Drill decompression	
Curettage/excision	
Arthrotomy	
Arthroscopy	
Amputation	

Debridement

Fasciotomy

Compartment decompression

Secondary closure

Skin graft

Other plastic surgery

1D: Summary of range of tests carried out and sensitivity of conventional microbiological tests. (Simple cases only)

TABLE 1D-1

N(%)
Children with at least one conventional test carried out
At least one micro-organism detected
Specific mirco-organisms detected by conventional testing:
Staphylococcus Aureus
PVL tested for?
Kingella Kingae
Streptococcus pyogenes
Pseudomonas
Group b Streptococcus
Salmonella
Candida
Tuberculosis
Other
PCR testing carried out

Types of sample used for conventional microbiological testing. (Simple cases only)

TABLE 1D-2

N(%)

Number of different
sample types taken

0

1

2

>2

Sample types. Children
that had at least one:

Pus (periosteal)

Bone biopsy

Pus/Wound swab

Joint aspirate

Other

1E: Blood-tests carried out at presentation. (Simple cases only)

TABLE 1E-1

Blood tests at presentation	N(%) with at least one measurement on day of presentation	Summary statistic for test results	% with elevated* results
Hb			
WCC			
N			
Plt			
CRP			
ESR			
CRP & ESR		-	-
CRP & not ESR		-	-
CRP _{max} occurring at presentation		-	-

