*Above the centre specific normal range

1F: Comparing average CRP_{max} for each culture negative vs. positive, by age-group. (PCR and conventional test results combined; Simple cases only).

TABLE 1F-1

Microbe	Summary statistics for CRP _{max}					
	< 1 year		1-6 years		6-16 years	
	+ve	-ve	+ve	-ve	+ve	-ve
Staphylococcus Aureus						
Kingella Kingae						
Streptococcus pyogenes						
Pseudomonas						
Group b Streptococcus						
Salmonella						
Candida						
Tuberculosis						
Other						

1G: Imaging types routinely used to aid diagnosis (On day of or prior to initiation of IV; Simple cases only).

TABLE 1G-1

Imaging Type	N(%) with at least one image	Number (%) Abnormal
X-ray		
CT scan		
Ultrasound		
MRI		
Bonescan		

What is the range of durations of intravenous and oral antibiotics used to treat osteomyelitis?

2A: The clinical time-line for antibiotic treatment.

TABLE 2A-1

Antibiotic Treatment Time-line (Days)	Appropriate Summary Statistics
Length of time on:	
IV	
Oral ^(a)	
Total ^(b)	

^(a)Use time on oral antibiotics pre-discharge plus planned duration, as proxy for actual duration.

^(b) Length of time treated with any antibiotic (for some children oral antibiotics were given concurrently to IV. So the Total length of time is not necessarily the time on IV plus the time on Oral)

Types of antibiotic regimes experienced.

TABLE 2A-2

Antibiotic Regime	All	Centre Type	
		Tertiary	Secondary
Number of different antibiotics given at initiation of treatment			
1			
2 or more			
Timing of oral switch			
Very Early (< 1 week)	Also report median & IQR		
Early (1-2 wks)	for each category		
Standard / Late (> 2 wks)	here		

Total course of antibiotics

Shortened (< 6 weeks)

Standard (> 6 weeks)

DoseAugmented at least once^(a)

Standard throughout

**Total number of antibiotics
prescribed****IV:**

1

2

>2

Oral:

1

2

>2

^(a)At least one IV antibiotic given at a high dose

2B: IV and oral antibiotics prescribed prior to discharge.

TABLE 2B-1

Antibiotic	Given at least once	Part of initial prescription	Daily dose per kg weight of child	Frequency					Duration (> 1 week)
				6 hourly	8 hourly	12 hourly	Once daily	Other	
IV									
Flucloxacillin									
Clindamycin									
Cefuroxime									
Ceftriaxone									
Other									
Oral									
Flucloxacillin									
Clindamycin									
Amoxicillin									
Co-Amoxiclav									
Rifampicin									

Other

TABLE 2B-2

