Antibiotics given as part of first treatment	Centre Type		Given had a penicillin allergy	Given had sickle cell disease
	Tertiary	Secondary		
IV				
Flucloxacillin				
Clindamycin				
Cefuroxime				
Ceftriaxone				
Other				
Oral				
Flucloxacillin				
Clindamycin				
Amoxicillin				
Co-Amoxiclav				
Rifampicin				
Other				

2C: Blood-tests carried out immediately prior to oral switch

TABLE 2C-1

Blood tests	Number (%) of cases with test results immediately prior to switch		Summary statistic for test results	As a proportion of CRP _{max}
	Tertiary	Secondary		
Hb				-
WCC				-
N				-
CRP				-
ESR				-
CRP & ESR			-	-
CRP & not ESR			-	-

2D: Surgery occurring after the initiation of IV antibiotics (post diagnosis).

TABLE 2D-1

Surgery types	Rate n (%)
All	
Aspiration	
Incision and drainage	
Drill decompression	
Curettage/excision	
Arthrotomy	
Arthroscopy	
Amputation	
Debridement	
Fasciotomy	
Compartment decompression	
Secondary closure	
Skin graft	
Other plastic surgery	

2E: Length of stay in hospital by age-group and site type.

TABLE 2E-1

Centre type	Age group			
	All	< 1 year	1-6 years	6-16 years
All				

Tertiary

Secondary

2F: Imaging types routinely used post diagnosis.

TABLE 2F-1

Imaging Type	Number (%) of cases imaged at least once post-diagnosis		Number (%) Abnormal
	Tertiary	Secondary	
X-ray			
CT scan			
Ultrasound			
MRI			
Bonescan			

2G: Antibiotic regimes prescribed at discharge. As part of this – what percentage went home on IV as opposed to oral antibiotics.

TABLE 2G-1

Antibiotic	N(%)	Daily dose per kg weight of child	Planned Duration
Went home on			
IV		-	-
Oral		-	-
IV			
Flucloxacillin			
Cefuroxime			
Ceftriaxone			
Benzyl Penicillin			
Other			
Oral			
Flucloxacillin			
Cefalexin			
Co-Amoxiclav			
Other			

2H: Were discharge antibiotic regimes adhered to? Percentages of treatments shortened or changed post discharge, split by who made the decision: parent, hospital or GP. What were the main reasons for non-adherence or change of regime post discharge?

TABLE 2H-1

Adherence to prescribed antibiotic regimes	Number (%)
Stopped early by:	

Parent
Hospital

GP

Changed by:

Hospital

GP

Reason for shortening / change of
regime:

Unpalatable antibiotic

Diarrhoea

Rash

Resolution of symptoms

Recurrence of infection

3A: Complication types by action taken.

TABLE 3A-1

Complication	N (%)	Action taken				
		None	Surgery	Change of antibiotic regime	Re-admission to hospital	Other action
Any Complications						

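### Imaging done after the first day of IV antibiotics can never count as aiding diagnosis, so Table 1G-1 understates diagnostic use of later modalities and Table 2F-1 mislabels those scans

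*SAP*

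**What the plan says.** Under Study Objectives, Objective 1 asks: "What are the clinical, biochemical and radiological criteria used by UK paediatricians / orthopaedic surgeons / radiologists to diagnose osteomyelitis". Sub-objective 1G narrows this to the imaging methods used to aid diagnosis and the proportion abnormal, with no time limit.

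Under Study Outcomes, the list of diagnosis endpoints makes IV start stand in for diagnosis: "Initiation of IV antibiotics [this time-point used also as a proxy for a diagnosis being made". Table 1B-1 repeats the proxy.

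The imaging analyses then divide at that point:

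- Analysis, Objective 1, item [1F] (the text behind Appendix Table 1G-1): "The number and percentage of cases for each imaging type used prior to diagnosis will be reported".
- Appendix A, heading of 1G: "Imaging types routinely used to aid diagnosis (On day of or prior to initiation of IV; Simple cases only".
- Analysis, Objective 2, item [2F]: "The number and percentage of cases with imaging after initiation of IV will be reported split by site type and image type".
- Appendix A, heading of 2F: "Imaging types routinely used post diagnosis".

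Analysis item [1B] and Table 1B-1 also list "Radiological diagnosis" as a time point of its own, next to initiation of IV antibiotics. The definitions of case groups include children treated for OM or SA who were later given a different diagnosis.

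**The concern.** The rule sorts scans by date relative to the first IV dose. It takes no account of a scan's purpose or of when the diagnosis was settled radiologically. If treatment starts on suspicion and a scan confirms the infection a day or more later, that scan is left out of the table meant to answer the imaging part of Objective 1 and appears in a table labelled as following diagnosis.

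At stake is the description of which imaging methods are used to reach the diagnosis. Methods that tend to come later lose counts and methods done on the first day do not. More cases would not correct this, because the loss comes from the definition and not from sampling.

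**Working it through.** The SAP states no figure that could be reproduced here, so the check traces the definition and then illustrates its effect.

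**1. One hypothetical child under the printed rules.** IV starts on day 0, an X-ray is done on day 0, and an MRI that establishes the diagnosis is done on day 2.

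| Table | What it records |
|---|---|
| 1B-1 | IV start on day 0; radiological diagnosis on day 2 |
| 1G-1 (aids diagnosis) | X-ray counted; MRI not counted |
| 2F-1 (post diagnosis) | MRI counted, with its abnormal result |

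Table 1B-1 would thus date the radiological diagnosis to day 2, while Table 1G-1 shows no MRI and Table 2F-1 treats the MRI as coming after diagnosis.

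**2. Can other tables recover the count?** No. Table 1B-1 gives time summaries and does not say which modality made the diagnosis. Table 2F-1 pools confirmatory scans with monitoring scans. Both imaging tables count cases with at least one image, so a case may appear in both, and neither adding nor subtracting them yields diagnostic use.

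**3. When does a late scan change the count?** Only when the child had no scan of that type on or before the day of IV start. Scans on that day stay in Table 1G-1. For the children affected, the effect goes one way: they can only be lost from the table.

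**4. Illustration of size (assumptions, not SAP data).** Let *m* be the true share of cases having a modality for diagnosis. Let *q* be the share of those whose only such scan falls after the day of IV start. Then

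reported use = *m* × (1 − *q*); cases lost = *N* × *m* × *q*.

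The value *N* = 500 is the minimum accrual expected under Sample size calculations. Table 1G-1 covers simple cases only, so its denominator may be smaller; the percentages do not depend on *N*.

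| Assumed *m* | *q* = 10% | *q* = 25% | *q* = 50% | 95% half-width at *m*, *N* = 500 |
|---|---|---|---|---|
| 40% | 36% (20 lost) | 30% (50 lost) | 20% (100 lost) | 4.3 points |
| 60% | 54% (30 lost) | 45% (75 lost) | 30% (150 lost) | 4.3 points |
| 80% | 72% (40 lost) | 60% (100 lost) | 40% (200 lost) | 3.5 points |

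Example: 0.60 × (1 − 0.10) = 54%, and 500 × 0.60 × 0.10 = 30 cases. The half-width is 1.96 × √(0.6 × 0.4 / 500) = 4.3 points. The shortfall exceeds the half-width in every cell except *m* = 40% with *q* = 10%, where it is 4 points against 4.3.

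**5. Percentage abnormal.** If a proportion *p*₁ of the counted cases and *p*₂ of the omitted cases are abnormal, the combined figure is a weighted average of the two. It lies above *p*₁ if *p*₂ is larger and below it if *p*₂ is smaller. The SAP gives neither, so the direction is open.

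**The case against.** The proxy is declared, in Study Outcomes and again in Table 1B-1, and the cut is printed in the headings of 1C, 1G and 2D. Sub-objective 2F and its analysis text describe the later scans neutrally as following IV start; only the Appendix carries the post-diagnosis label. Same-day scans are kept, and later scans are still reported with their abnormal counts. For a descriptive service evaluation this is a coarse but visible working definition.

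All of that is true, and it means nothing is concealed. It does not make the definition answer Objective 1. Confirmatory scans cannot be separated out of Table 2F-1, and the label there asserts something the rule does not establish.

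A second objection is that the radiological diagnosis date is no ready-made gold standard. This stands. The event is undefined in the SAP and absent from the key actions in sub-objective 1B and from the diagnosis endpoints. Data Collection names radiological procedures, not such a date. Entry is by clinical diagnosis, so some children may have no such date. It therefore belongs in an added column with its missingness shown, not in place of the present cut.

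A reader might also infer that the tertiary/secondary comparison is distorted because referred children arrive already on IV. The SAP does not say so. It records transfers between hospitals and measures times from first presentation, so imaging before IV at the first hospital may well be captured, and imaging at the receiving hospital may truly follow diagnosis.

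**Conclusion.** The concern holds as a poor choice of definition. A child whose only scan of a given type that established the diagnosis was done after the day of IV start is missing from Table 1G-1 for that modality, and the scan is labelled as post-diagnosis imaging. Diagnostic use is understated whenever such children exist. The SAP gives reason to expect them: it times radiological diagnosis separately from IV start and provides for treated children whose diagnosis was later revised.

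The size cannot be derived from the SAP. The table under the working only shows what assumed shares of 10% to 50% would do.

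Two stronger readings are tempting and not supported. One is that Objective 1 as a whole is answered wrongly: imaging is one part of it, the rule is visible, and the loss may be small if few first scans of a type follow IV start. The other is that abnormal rates are understated: they may move in either direction.

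**What to change.** **Table 1G-1.** Keep the present column (on or before IV start). Add a column counting imaging up to and including the date of radiological diagnosis, or up to IV start if that is later or the date is missing. Because this cut is never earlier than IV start, the added column can only equal or exceed the present one, and the difference shows directly what the proxy leaves out. State the number of children lacking the date. Footnote that the abnormal rate among the added scans is selected, since that window closes with the radiological diagnosis.

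**Table 2F-1.** Keep it as all imaging after IV start, as sub-objective 2F requires. Change the heading and column label to say after initiation of IV instead of post diagnosis. Show separately the scans done up to the radiological diagnosis date.

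**Text.** Define radiological diagnosis once, at analysis item [1B], and use that definition in both tables.

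**Cost.** Some wording, one extra column in each imaging table, and a check that the date is held, which Table 1B-1 already needs. The diagnosis cut for imaging will then differ from the IV-start cut kept for surgery in Tables 1C-1 and 2D-1; a note should say so.
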